2.2. Rationale

Current Limitations of Knowledge or Therapy in Pancreatic Cancer:

Pancreatic cancer is the third leading cause of cancer death, and its prognosis is grim: 5-year survival rate being 6-8%³. Due to a lack of treatment options, gemcitabine became the reference regimen for advanced pancreatic cancer for many years, even though gemzar alone offers only marginal improvement in overall survival (5.6 vs. 4.4 months, gemzar vs. fluorouracil)¹⁶. The combination of gemzar with a variety of cytotoxic and targeted agents has generally shown no significant survival advantage as compared with gemzar alone¹³. Some clinical studies have suggested a benefit with gemzar -based cytotoxic combinations in patients with good performance status¹⁶. However, gemzar -based cytotoxic combinations are very toxic and patients experience poor quality of life during treatment. The most promising results reported to date is FFX (a 4-drug combination of 5-FU, folinic acid, irinotecan and oxaliplatin)¹², and the

nab-paclitaxel + gemzar combination¹³, which provide a median overall survival of 11.1 months and 8.5 months, respectively, in metastatic pancreatic cancer patients. However, these drugs have high toxicity and only patients with favorable performance status are eligible to receive these regimens. Although these drugs significantly improve patient survival, the median overall survival of approximately 11 months in patients with good performance status is still unsatisfactory. A safer and more effective therapy for advanced pancreatic cancer is currently an active area of research and development.

Importance of the study:

Given the favorable safety and efficacy profiles of devimistat when administered in combination with mFFX along with the promising efficacy results achieved in trial CCCWFU57112, the further evaluation of devimistat in pancreatic cancer was warranted. Based on the experience in phase I study, Rafael Pharmaceuticals will initiate a phase III randomized trial of standard dose FFX versus devimistat + mFFX¹⁷ in patients with metastatic adenocarcinoma of the pancreas. The goal of this trial is to provide compelling evidence of the safety and efficacy of this approach leading to a regulatory approval for devimistat in combination with mFFX for use in patients with metastatic adenocarcinoma of pancreas and has the potential to address serious medical unmet needs for this indication.

2.3. Risk/Benefit Assessment

Please refer to the appendix III for study-specific assessment for details.

Primary Objective:

- To determine efficacy of devimistat plus mFFX compared to standard care FFX in terms of **Overall Survival (OS)**

Secondary Objectives:

- To determine efficacy of devimistat plus mFFX compared to standard care FFX in terms of **Progression-Free Survival (PFS)**.
- To determine efficacy of devimistat plus modified FOLFIRINOX (mFFX) compared to standard care FOLFIRINOX (FFX) in terms of **Objective Response Rate (ORR)**. ORR is defined as Complete Response (CR) plus Partial Response (PR).
- To evaluate **Duration of Response (DOR)**
- **Safety Analysis:** The assessment of safety will be based mainly on the frequency of adverse events based on the Common Terminology Criteria for Adverse Events (CTCAE version 4) grade. Adverse events will be coded according to MedDRA. The safety outcomes will include the occurrence of at least one serious adverse event, of at least one grade 3/4 adverse event, and of at least one adverse event requiring the discontinuation of study treatment. **QTc** intervals will be also evaluated as part of safety analysis.
- To assess **PK** of devimistat.
- To evaluate **Patient-Reported Outcomes (PRO)** for devimistat plus mFFX compared to standard care FFX.

Exploratory Objectives:

- To explore **biomarkers** using diagnostic biopsies and blood/plasma samples.
- To assess **PK/PD** of **dose/exposure-response** for devimistat on efficacy (e.g. PFS), safety (e.g. QTc) and exploratory biomarkers.

4.1. Description of the Study Design

This is a prospective, **multicenter, open label, randomized Phase III** study of **CPI-613[®] (devimistat) + mFFX** compared to **FFX** in patients with metastatic (Stage IV) adenocarcinoma of the pancreas with age range of 18 to 75 years.

There will be **two study arms**:

1. **Arm 1:** devimistat + mFFX
2. **Arm 2:** FFX

Subjects will be randomized in 1:1 ratio to the experimental treatment or control, using a minimization procedure (Buyse, 2000)²⁰. The minimization algorithm will use the variance method to minimize overall imbalances between the treatment arms with respect to site, performance status (0 vs. 1), and primary tumor location (head vs. body vs. tail of the pancreas).

4.2. Study Endpoints

4.2.1. Primary Endpoints

This study has one primary endpoint:

Overall Survival (OS), defined as the duration from the date of randomization to the date of death from any cause.

4.2.2. Secondary Endpoints

This study has six secondary endpoints:

- **Progression-Free Survival (PFS)**, defined as the duration from the date of randomization to the date of progressive disease (assessed by an independent, blinded, central review) or death from any cause. PFS will be confirmed by investigator's assessment with the intent to perform sensitivity analyses.
- **Objective Response Rate (ORR)**, defined as the rate of Complete Response (CR) plus Partial Response (PR). A patient's best response within the first 12 cycles will be used for this determination, as assessed by independent, blinded, central review as per RECIST guideline version 1.1.¹⁸ ORR will be confirmed by investigator's assessment with the intent to perform sensitivity analyses.

- **Duration of Response (DOR)**
- **Safety: AEs, SAEs, QTc.**
- **Pharmacokinetics:** Full PK – C_{max} , T_{max} , AUC_{0-t} , AUC_{inf} , CL, V, $T_{1/2}$; Sparse PK – concentrations from Sparse PK sampling plus concentrations from Full PK sampling time points to be used for Population PK analysis
- **Patient-Reported Outcomes (PRO):** At baseline and day 1 of every even numbered cycle, patient will be required to complete one self-administered quality of life instrument.

NCCN-FACT FHSI-18 is a widely used PRO questionnaire for patients with hepatobiliary cancer (liver, bile duct and pancreas) developed by FACIT.org available at: <http://www.facit.org/FACITOrg/Questionnaires>. Summary statistics of the scores will be shown by cycle (pre and post treatment). Scores will be compared between standard and study arms. Efforts to avoid missing data will include data collection to be done during follow up clinic visits only and no additional visits will be required to complete the questionnaire. Additionally, only the validated, user friendly version of the questionnaire will be used for data collection.

4.2.3. Exploratory Endpoints

- **Exploratory biomarkers:** 10 unstained slides from baseline and time of progression biopsies will be collected when available. These slides will be used for IHC staining for PDKs, PDH, KGDH, SOD2 and CD79a. They will also be used as a source of material for RNA and whole exome sequencing. Additionally, blood samples will be used as a source of circulating tumor cells and germline DNA for SNP analysis for predictors of response, resistance or toxicity. Serum samples will be utilized to analyze the concentrations of systemic metabolites.
- **PK/PD:** dose/exposure-response of devimistat on efficacy (e.g. PFS), safety (e.g. QT) and exploratory biomarkers.

5.1. Inclusion Criteria

In order to be eligible to participate in this study, an individual must meet **all** of the following criteria:

- 5.1.1 Histologically or cytologically confirmed metastatic Stage IV adenocarcinoma of the pancreas
- 5.1.2 No prior treatments for stage IV pancreatic adenocarcinoma (prior adjuvant or neoadjuvant treatment is allowed provided completed \geq 6 months prior to disease recurrence)
- 5.1.3 Eastern Cooperative Oncology Group (ECOG) performance status 0 – 1¹⁷
- 5.1.4 Male and female patients 18 – 75 years of age
- 5.1.5 Measurable disease determined using guidelines of Response Evaluation Criteria In Solid Tumors (RECIST version 1.1)
- 5.1.6 Expected survival >3 months
- 5.1.7 Women of child-bearing potential (i.e., women who are pre-menopausal or not surgically sterile) must use accepted highly effective contraceptive methods (abstinence, intrauterine device [IUD], oral contraceptive(s), intrauterine hormone releasing system (IUS), bilateral tubal occlusion or vasectomized partner) during and for 6 months after last study dose and must have a negative serum or urine pregnancy test within 1 week prior to treatment initiation, at monthly interval (*day 1 of every even numbered cycle*), at the end of systemic exposure, and at 30 days after the systemic exposure
- 5.1.8 Males with female partners (of childbearing potential) and female partners (of child bearing potential) with male partners must agree to use double barrier contraceptive measure (a combination of male condom with either cap, diaphragm or sponge with spermicide) in addition to oral contraception or avoidance of intercourse during the study and for 6 months after last study dose is received
- 5.1.9 At least 2 weeks must have elapsed from any prior surgery with resolution of any sequela for randomization
- 5.1.10 Laboratory values \leq 2 weeks prior to randomization must be:
 - Adequate hematologic values
 - Platelet count \geq 100,000 cells/mm³ or \geq 100 bil/L:
 - Absolute neutrophil count [ANC] \geq 1,500 cells/mm³ or \geq 1.5 bil/L:

- Hemoglobin ≥ 9 g/dL or ≥ 90 g/L)
- Adequate hepatic function
 - Aspartate aminotransferase [AST/SGOT] ≤ 3 x upper normal limit [UNL] (≤ 5 x UNL if liver metastases present)
 - Alanine aminotransferase [ALT/SGPT] ≤ 3 x UNL (≤ 5 x UNL if liver metastases present)
 - Bilirubin (≤ 1.5 x UNL); bilirubin ≤ 2.5 x ULN for subjects with Gilbert's syndrome
 - Serum albumin ≥ 3.0 g/dL
- Adequate renal function
serum creatinine clearance $CL_{cr} > 30$ mL/min). (Cocroft-Gault Formula should be used for CrCl calculation)
- Adequate coagulation function
International Normalized Ratio or INR must be < 1.5 unless on therapeutic blood thinners).

5.1.11 No evidence of active infection and no serious infection within the past 30 days.

5.1.12 Mentally competent, ability to understand and willingness to sign the informed consent form

5.2. Exclusion Criteria

An individual who meets **any** of the following criteria will be excluded from participation in this study:

5.2.1 Endocrine or acinar pancreatic carcinoma

5.2.2 Known cerebral metastases, central nervous system (CNS), or epidural tumor

5.2.3 Prior treatment with any chemotherapy for metastatic adenocarcinoma of the pancreas

5.2.4 Completion of a gemcitabine-based adjuvant chemotherapy regimen within less than 6 months at the time of screening.

5.2.5 Receipt of neoadjuvant or adjuvant FOLFIRINOX therapy if < 6 months prior to disease recurrence

5.2.6 Patients with hypersensitivity to devimistat, FFX treatment or any of their excipients

5.2.7 Presence of clinically significant abdominal ascites

5.2.8 Patients receiving any other standard or investigational treatment for their cancer, or any other investigational agent for any indication within the past 2 weeks prior to initiation of

devimistat treatment

- 5.2.9 Serious medical illness that would potentially increase patients' risk for toxicity
- 5.2.10 Any active uncontrolled bleeding, and any patients with a bleeding diathesis (e.g., active peptic ulcer disease)
- 5.2.11 Female patients who are pregnant or breastfeeding or planning to become pregnant or breastfeed during treatment and for an additional 6 months after the last dose of study treatment
- 5.2.12 Female patients of childbearing potential with a positive pregnancy test assessed by a serum pregnancy test at screening
- 5.2.13 Female patients of childbearing potential unwilling to use 1 highly effective method of contraception during treatment and for 6 months after the last dose of study treatment
- 5.2.14 Male patients with a pregnant partner who are unwilling to practice abstinence or use a condom during treatment and for 6 months after completion of study treatment
- 5.2.15 Male patients unwilling to abstain from donating sperm during treatment and for 6 months after completion of study treatment
- 5.2.16 Life expectancy less than 3 months
- 5.2.17 Any condition or abnormality which may, in the opinion of the investigator, compromise the safety of patients
- 5.2.18 Unwilling or unable to follow protocol requirements
- 5.2.19 Active heart disease including but not limited to symptomatic congestive heart failure (NYHA class 3 or 4), symptomatic coronary artery disease, symptomatic angina pectoris, or symptomatic myocardial infarction
- 5.2.20 Patients with a history of myocardial infarction that is <3 months prior to registration
- 5.2.21 Evidence of active infection, or serious infection within the past 30 days.
- 5.2.22 Patients with known HIV infection
- 5.2.23 Patients who have received cancer immunotherapy of any type within the past 2 weeks prior to initiation of devimistat treatment (steroids given for supportive care or in response to allergic reactions are allowed at any time)
- 5.2.24 Requirement for immediate palliative surgery, radiation or chemotherapy of any kind. Stenting for bile duct obstruction and need for pain medications are allowed provided all other inclusion criteria are met
- 5.2.25 Prior malignancy except for the following: adequately treated basal or squamous cell skin cancer, *in situ* cervical cancer, adequately treated cancer from which the patient has been disease-free for at least 3 years prior to screening

- 5.2.26 Unwilling or unable to avoid the concomitant use of strong CYP3A4 inducers or inhibitors during treatment with irinotecan
- 5.2.27 A marked baseline prolongation of QT/QTc interval (e.g., repeated demonstration of a QTc interval > 480 milliseconds (ms) (CTCAE grade 1) using Fredericia's QT correction formula (i.e. QTcF)
- 5.2.28 A history of additional risk factors for TdP (e.g., heart failure, hypokalemia, family history of long QT syndrome)
- 5.2.29 The use of concomitant medications that prolong the QT/QTc intervals are excluded at screening and C1D1
- 5.2.30 Contraindications to any of the FFX treatment as follows:

Folinic Acid

- Calcium Folate is contraindicated in patients who have previously shown hypersensitivity to folinate or any of the excipients.
- Calcium Folate Injection is contraindicated in the treatment of pernicious anemia or other megaloblastic anemias where vitamin B12 is deficient. Its use can lead to an apparent response of the hematopoietic system, but neurological damage may occur or progress if already present.
- Patients with rare hereditary problems of galactose intolerance, the Lapp lactase deficiency or glucose-galactose malabsorption should not take calcium folinate tablets.

5FU/ Fluorouracil

- Fluorouracil is contraindicated in patients who have any known hypersensitivity to fluorouracil, are seriously debilitated or are suffering from bone marrow depression after radiotherapy or treatment with other antineoplastic agents, or who are suffering from a potentially serious infection.
- Fluorouracil is strictly contraindicated in pregnant or breast-feeding women.
- Fluorouracil should not be used in the management of non-malignant disease.
- Fluorouracil must not be taken or used concomitantly with brivudin, sorivudine and analogues. Brivudin, sorivudine and

analogues are potent inhibitors of the enzyme dihydropyrimidine dehydrogenase (DPD) which degrades fluorouracil

- In patients with known complete absence of dihydropyrimidine dehydrogenase (DPD) activity

Oxaliplatin

- Oxaliplatin is contraindicated in patients who have a known history of hypersensitivity to oxaliplatin or to any of the excipients
- are breast-feeding.
- have myelosuppression prior to starting first course, as evidenced by baseline neutrophils $<2 \times 10^9/l$ and/or platelet count of $<100 \times 10^9/l$.
- have a peripheral sensitive neuropathy with functional impairment prior to first course.
- have a severely impaired renal function (creatinine clearance less than 30 ml /min)

Irinotecan

- Chronic inflammatory bowel disease and/or bowel obstruction
- History of severe hypersensitivity reactions to Irinotecan hydrochloride trihydrate or to any of the excipients
- Bilirubin > 3 times the ULN
- Severe bone marrow failure.
- WHO performance status > 2 .
- Concomitant use with St John's wort

5.3. End of Treatment

Subjects should return to the study site for an End of Treatment Visit within approximately 7 days after treatment discontinuation of all study medication (CPI 613[®] + mFFX or FFX) and prior to initiation of subsequent anticancer therapy. Adverse events and concomitant medications will be reviewed at this visit, and the following assessments should be completed:

- Physical Examinations
- Vital Signs
- ECOG Performance Status
- Weight/BSA
- Obtain CT scan (or MRI) if radiologic disease progression was not documented in the previous CT scan (or MRI) unless the latter one was performed within the last 14 days
- Blood sample collection for the following tests: Hematology, Blood Chemistry, and CA 19-9
- Collect AE and SAE
- Pregnancy test
- NCCN-FACT FHSI-18 Questionnaire

5.3.1. Discontinuation of Treatment

The Investigator must protect the subject's welfare and may discontinue any study treatment at any time when this action appears to be in the subject's best interest. The reason for the subject's discontinuation must be recorded in the subject's electronic case report. Possible reasons for the discontinuation may include, but are not limited to, the following:

- Disease Progression defined as follow: disease progression documented by CT scan (or MRI) based on RECIST version 1.1 criteria, as determined in the protocol;
- Adverse Event;
- Any significant Protocol Violation as per protocol;
- Withdrawal of consent by an enrolled subject.

5.3.1.1 Patients requiring delay for more than 3 weeks because of toxicity.

- 5.3.1.2 Unacceptable toxicity from FFX or mFFX + devimistat (Grade 3 or more severity of toxicity).
- 5.3.1.3 The subject becomes pregnant (treatment should be discontinued immediately)
Intercurrent illness with a condition, injury, or disease unrelated to the intended disease for which the study is investigating, that renders continuing the treatment unsafe or regular follow-up impossible.
- 5.3.1.4 General or specific changes in the patient's condition that in the opinion of the treating physician renders the patient ineligible for further investigational treatment.
- 5.3.1.5 Recurrent grade 4 adverse events despite all appropriate dose reductions.
- 5.3.1.6 Non-compliance with investigational treatment, protocol-required evaluations or follow-up visits.
- 5.3.1.7 Other reasons as determined by the Investigator or Sponsor: A subject may have study treatment discontinued if, in the opinion of the Investigator or Sponsor, it is not in the subject's best interest to continue; Unambiguous clinical progression documented by the Investigator in the absence of radiological confirmation.

Subjects who discontinue all study medication for any reason should remain in the study for long-term follow up assessments unless they withdraw informed consent, die, or become lost to follow up. Long-term follow up evaluations will be performed accordingly as described in the protocol. In the event of study treatment discontinuation, the subject should be instructed to report to the site as early as possible after the decision to discontinue study treatment has been made. All End of Treatment procedures should be performed according to the protocol.

When discontinuing study treatment during this trial, the investigator should make every effort to contact the patient and to perform an End of Treatment (EOT) evaluation. Also, the reason(s) for withdrawal from the study must be recorded. Survival and post-study treatment will be documented bi-monthly after patient completes treatment on this trial. All patients will be followed until the number of events met for the primary endpoint and database is locked.

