Cycle 1	Day 1	
Devimistat: IV infusion at the rate of 4 mL/min at the dose of 500 mg/m² concurrently with D5W at the rate of 125mL/hour (2.08mL/min) via a central venous catheter
 
mFFX (given immediately after devimistat administration):
 
 - Oxaliplatin at 65 mg/m² given as a 2-hr IV infusion - Folinic acid at 400 mg/m² given as a 90-min (1.5 hr) infusion immediately after oxaliplatin, and concurrently with Irinotecan at 140 mg/m² given as a 90-min IV infusion via a Y-connector. - Flurouracil (5-FU) at 400 mg/m² as bolus followed by a 42-48-hr infusion at 2,400 mg/m², starting immediately after completion of folinic acid and irinotecan
	Day 2	
mFFX:
 
 - Completing the remaining of the 5-FU 42-48-hr infusion starting on Day 1
	Day 3	
mFFX:
 
 - Completing the remaining of the 5-FU 42-48-hr infusion starting on Day 1, 2 and disconnect the 5-FU pump. 
devimistat:
 
 - Devimistat (500 mg/m²), IV infusion at the rate of 4 mL/min via a central venous catheter after completion of 5-FU infusion. Devimistat infusion must be administered concurrently with D5W at the rate of 125mL/hour (2.08mL/min) via a central venous catheter. In the event that time will not permit devimistat administration following 5-FU infusion, devimistat may be administered concurrently with 5-FU via a double lumen port.
	Day 4 (-/+ 24 hours)	Myeloid Growth factor per institutional guidelines
	Days 5 -14	No treatment
Cycle 2 and subsequent Cycles (every 2 weeks)		Same as Cycle 1

Dosing as above will continue for at least 6 months in responding patients with acceptable tolerance to therapy (with dose modifications per protocol as needed) unless a criterion for removal from study occurs. Responding patients upon completion of at least 10 cycles and after having two sequential CT scans showing stable disease (no continued decrease in lesion size) will complete 2 additional cycles (to complete a minimum of 12 cycles) of their assigned treatment.

Following 12 cycle and all the subsequent cycles oxaliplatin can be dropped at the discretion of the treating physician if not already omitted. Cycles will continue until one of the criteria for removal from study are reached (Section 5.3.1).

FOLFIRINOX (Control Arm 2; FFX):

Calculation of the Amount of FOLFIRINOX for Each Patient:

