6.1.6. Dose Adjustments/Modifications/Delays

No dose modifications are allowed for devimistat in this study.

The dose of Folinic Acid is not modified for any toxicity but is omitted if fluorouracil is omitted. Once a dose of any of the drugs comprising FFX is decreased, re-escalation of the dose is not permitted. Patients are taken off the study if they develop the same Grade 4 toxicity despite dose reduction. The dose adjustment scheme for FFX is dependent on the type of toxicities, as described below.

Hematologic Toxicity

Once hematologic toxicity is observed in a patient, do not retreat the patient with mFFX or FFX until the absolute neutrophil count is $\geq 1.5 \times 10^9/L$ and the platelet count is $\geq 75 \times 10^9/L$. The dose modification schemes for FFX related to hematologic toxicity are shown in Table 9.

Primary prophylaxis with myeloid growth factor will be at the discretion of the treating physician and as per the ASCO guidelines. If the patient is not being treated with myeloid growth factor the initial modification for neutropenia should be the addition of a myeloid growth factor. If the patient is already on a myeloid growth factor, then dose adjustments are as outlined in Table 9.

Table 9 Dose Modifications for Hematological Toxicities on Day 1 of a Cycle. Cycles are Every Two Weeks.

Day 1	Delay the Start of a Treatment Cycle*	Doses Reduction		
		Irinotecan	Oxaliplatin	Fluorouracil (5-FU)
ANC <1.5x10 ⁹ /L	Withhold treatment until granulocytes ≥1.5x10 ⁹ /L.	1 st occurrence: Continue same dose	1 st occurrence: Continue same dose	1 st occurrence: Delete bolus 5-FU
		2 nd occurrence: Reduce to 80% of starting dose	2 nd occurrence: Continue same dose	
		3 rd occurrence: Reduce to 50% of starting dose	3 rd occurrence: Reduce to 80% of starting dose	
		4 th occurrence: Discontinue irinotecan	4 th occurrence: Continue on 80% of starting dose	
Platelets <75x10 ⁹ /L	Withhold treatment until platelets ≥75x10 ⁹ /L.	1 st occurrence: No dose reduction	1 st occurrence: No dose reduction	1 st occurrence: Delete bolus 5-FU
		2 nd occurrence: Reduce to 80% of starting dose	2 nd occurrence: Reduce to 80% of starting dose	
		3 rd occurrence: Reduce to 50% of starting dose	3 rd occurrence: Discontinue oxaliplatin	
		4 th occurrence: Discontinue irinotecan	4 th occurrence: Discontinue oxaliplatin	

Table 10 Dose Adjustments According to Non-Hematological Toxicities (Excluding Alopecia, Nausea and Vomiting).

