Adverse Events	Dose Reduction for Subsequent Treatment Cycles

Diarrhea Grade 3-4, or diarrhea + fever and/or neutropenia Grade 3-4
 
Patients must be instructed in the use of loperamide as treatment for diarrhea and must have a supply of this drug upon starting treatment. Patients should not be retreated with irinotecan until diarrhea is \leq Grade 1 (without loperamide for at least 24 hrs.).
 
If acute cholinergic syndrome appears (defined as early diarrhea and certain other signs and symptoms such as sweating, abdominal cramps, miosis and salivation), atropine sulphate (0.25 mg subcutaneously) should be administered unless clinically contraindicated. In patients who experienced an acute and severe cholinergic syndrome, the use of prophylactic atropine sulphate is recommended with subsequent doses of Irinotecan hydrochloride.
	
1st occurrence: Reduce the irinotecan dose to 80% of the original dose and delete the bolus 5-FU dose
 
2nd occurrence: Reduce also the oxaliplatin dose to 80% of the original dose AND reduce the dose of continuous 5-FU to 75 % of the original dose
 
3rd occurrence: Discontinue treatment

Mucositis or “Hand-Foot” Syndrome
	
Grade 1-2 toxicity - continue on same doses of drugs
 
Grade 3-4 toxicity - delete bolus 5-FU and a reduction of 25% in continuous 5-FU doses in subsequent treatment cycles.
 
If mucositis is related to oxaliplatin, delay oxaliplatin or modify the dose until the toxicity grade \leq 1.

Myocardial Ischemia – Monitored by Cardiac Enzymes (CK/CKMB, TP)
	
5-FU must be permanently discontinued.

Hyperbilirubinemia
	
Obstruction of the biliary system or progressive disease must be established, and the treatment cycle delayed if the cause is biliary obstruction that can be addressed to reduce the hyperbilirubinemia. If bilirubin is persistently $>1.5x$ of Upper Limit of Normal (ULN), irinotecan must be omitted. If there is no potentially reversible obstruction, then irinotecan must be discontinued.

Other Toxicities
	
To be discussed with Medical Director.

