7.1. Study Procedures/Evaluations

7.1.1. Study Specific Procedures

Medical History:

Will be obtained by direct interview with the patient during the course of standard clinic visits or hospital admission.

Physical Examination:

Will be obtained during the course of standard clinic visits or hospital admission.

ECOG Performance Status scales¹⁹ will be used to assess how a patient's disease is progressing and assess how the disease affects the daily living abilities of the patient. The scale is listed in Table 11 below.

Table 11 Scales Used in ECOG Performance Status Grade

ECOG Score	Description
0	Fully active, able to carry on all pre-disease performance without restriction
1	Restricted in physically strenuous activity but ambulatory and able to carry out work of a light or sedentary nature, e.g., light housework, office work
2	Ambulatory and capable of all self-care but unable to carry out any work activities. Up and about more than 50% of waking hours
3	Capable of only limited self-care, confined to bed or chair more than 50% of waking hours
4	Completely disabled. Cannot carry on any self-care. Totally confined to bed or chair
5	Dead

Radiographic or Other Imaging Assessments:

Tumor Assessment:

Objective response assessment will be determined by triphasic contrast CT of the chest abdomen and pelvis as per RECIST guideline version 1.1 every 8 weeks +/-7 days while patients are on treatment. MRI assessments of tumor status may replace CT scans if needed for tumor response evaluation. However, the same imaging modality must be followed serially. Target lesions will be identified and documented prospectively from the baseline scan prior to assessments of any follow up scans. Each tumor lesion will be assigned a unique identifier consisting of the patient

study ID number followed by a letter. Should a lesion completely resolve during treatment that lesion will be scored as a 0 (zero) and not left blank to ensure lesion resolution is accurate and not a reflection of missing data. The timing and location of any new lesions will be recorded upon evaluation of the first scan to demonstrate this lesion. Patients will continue on assigned treatment until one of the stopping criteria are met (see Section 5.3.1). Patients who are allergic to contrast should get an MRI and those allergic to both, they can get a non-contrasted study.

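### Protocol 5.3.1.2 ties unacceptable toxicity to Grade 3 or more, Table 10 reduces doses and continues after Grade 3-4 events, and no passage says which takes precedence

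*Protocol*

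**What the plan says.** Four groups of statements in the current Protocol bear on this.

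- **Section 5.3.1, Discontinuation of Treatment.** The list opens with "Possible reasons for the discontinuation may include, but are not limited to, the following". Item 5.3.1.2 is "Unacceptable toxicity from FFX or mFFX + devimistat (Grade 3 or more severity of toxicity". Item 5.3.1.5, in the same list, is "Recurrent grade 4 adverse events despite all appropriate dose reductions".
- **Cross-references to 5.3.1.** Section 6.1.5 says, for Arm 1, "Cycles will continue until one of the criteria for removal from study are reached (Section 5.3.1", and says the same for Arm 2. Section 7.3.2 repeats it under duration of treatment. Section 7.1.1, on tumor assessment, says "Patients will continue on assigned treatment until one of the stopping criteria are met (see Section 5.3.1". Section 7.3.3 refers to 5.3.1 again for cycles beyond Cycle 12.
- **Section 6.1.6, text.** "Patients are taken off the study if they develop the same Grade 4 toxicity despite dose reduction".
- **Section 6.1.6, Table 10.** Grade 3-4 diarrhea leads to dose reductions at the first and second occurrences and to discontinuation at the third. For mucositis or hand-foot syndrome the instruction is "Grade 3-4 toxicity - delete bolus 5-FU and a reduction of 25% in continuous 5-FU doses in subsequent treatment cycles". Toxicities without their own row are to be discussed with the Medical Director.

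**The concern.** Taken at its word, the parenthesis in 5.3.1.2 makes a first Grade 3 toxicity from study treatment a reason to stop. Table 10 tells the site to reduce and continue after some of those same events. If a single Grade 3 event did end treatment, the Grade 3-4 instructions in Table 10, the Grade 4 rule in 6.1.6 and item 5.3.1.5 would have little or nothing left to act on.

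The trial is open-label, so the choice is made by someone who knows the arm. At stake are how patients are managed, whether exposure is comparable across sites, and whether reasons for discontinuation and protocol deviations are recorded on a common basis.

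**Working it through.** The conflict is textual and no design figure changes. The check has three parts.

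**1. The same event under each passage**

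- *First Grade 3 diarrhea attributed to study treatment.* Item 5.3.1.2, read literally: a reason to stop. Table 10: reduce and continue. Section 6.1.6 text and item 5.3.1.5: not triggered, because the event is neither Grade 4 nor a repeat.
- *First Grade 3 mucositis or hand-foot syndrome.* Same split: 5.3.1.2 gives a reason to stop, and Table 10 continues at reduced fluorouracil.
- *Grade 3 hyperglycemia or sensory neuropathy.* Table 10 has no row for either, so both fall under its category of other toxicities. Item 5.3.1.2 is then the only written grade threshold below the Grade 4 rules.
- *Low neutrophils or platelets.* Table 9 is keyed to counts and states no grades, so no explicit conflict is shown there.

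**2. Is 5.3.1 mandatory or discretionary?**

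The lead-in points to discretion. The references in 6.1.5, 7.1.1, 7.3.2 and 7.3.3 use 5.3.1 as the place where the end of treatment is defined. No passage settles it.

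**3. Scale, from the Protocol's own phase I data**

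Inputs: Appendix III, 18 patients at 500 mg/m² devimistat with modified FOLFIRINOX; Grade 3-4 hyperglycemia in 10, Grade 3-4 diarrhea in 5. The Protocol plans 250 patients in Arm 1. The exact (Clopper-Pearson) 95% interval for x of n runs from the 0.025 quantile of Beta(x, n − x + 1) to the 0.975 quantile of Beta(x + 1, n − x).

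- Hyperglycemia: 10/18 = 0.556, which reproduces the stated 55% apart from rounding. Interval: Beta(10, 9) gives 0.308 and Beta(11, 8) gives 0.785. On 250 patients: 250 × 0.556 = 139, range 250 × 0.308 = 77 to 250 × 0.785 = 196.
- Diarrhea, which does have a Table 10 row: 5/18 = 0.278, matching the stated 28%. Interval 0.097 to 0.535. On 250 patients: 69, range 24 to 134.

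Attribution limits the first figure. Item 5.3.1.2 concerns toxicity from the study regimens, and Appendix III does not restrict its counts to related events. Table 5, at a different data cut-off, gives treatment-related hyperglycemia of all grades as 45% of 20, that is 0.45 × 20 = 9 patients. If all nine were Grade 3-4 and at this dose, the related rate would be 9/18 = 50%. The documents give no Grade 3-4 rates for the FFX control, so no between-arm difference can be computed.

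**The case against.** The best defense is that 5.3.1 is a list of reasons open to the investigator. Its lead-in is permissive, unacceptable is a word of judgment, and the Grade 3 parenthesis can be read as a floor below which toxicity is not unacceptable. The same list contains adverse event with no grade at all; if the cross-references made every item mandatory, any Grade 1 event would end treatment. The dosing paragraphs in 6.1.5 also allow for dose modifications, 5.3.1.5 presupposes dose reductions, and Table 10 is the more specific instruction.

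This shows that a discretionary reading is available and perhaps intended. It does not remove the conflict. If the list is only discretionary, the sections that send the reader to 5.3.1 for stopping criteria point to no defined criterion. If it is mandatory, 5.3.1.2 overrides Table 10. That the specific instruction should prevail is an inference, since precedence is not stated.

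A second objection also stands: investigators may stop treatment at any time in the patient's interest, so some variation between sites would remain after any rewording. The wording can remove only the part that comes from the Protocol disagreeing with itself.

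A reader might go further and infer that any Grade 3 event must end treatment, or that only recurrent Grade 4 events do. Neither follows: 5.3.1.2 is qualified by unacceptable, and 5.3.1.5 is one item among several.

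**Conclusion.** The concern holds as an internal inconsistency. Item 5.3.1.2 conflicts with Table 10 and sits badly with 6.1.6 and 5.3.1.5. The Protocol uses 5.3.1 both as a list of possible reasons and as the stopping criteria, and states no precedence. Sites could therefore stop or continue on the same Grade 3 event, with consequences for patient care, exposure and the recording of discontinuations and deviations.

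On size, the phase I figures show that a literal reading could reach a substantial share of Arm 1. A reader might infer that it would stop more than half. The documents do not support that: the 55.6% comes from 18 patients, its interval runs from 31% to 78%, and it is not limited to related events.

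A reader might also infer a biased treatment effect. That is not shown either. Overall survival is analyzed by intention to treat, with a treatment-policy strategy for discontinuation (SAP 6.2.1), so the test stays valid. The PFS estimand (SAP 6.3.1) also handles discontinuation by treatment policy, so stopping does not itself censor. An indirect route exists: Protocol 7.1.1 specifies the 8-weekly scans for patients on treatment, 7.3.5 allows progression to be collected afterward by chart review or telephone, and the SAP censors events that follow new anticancer therapy or two missed scans. The documents do not allow the size or direction of any such effect to be computed.

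**What to change.** Reconcile 5.3.1.2 with 5.3.1.5, the text of 6.1.6 and Table 10, so that a given toxicity grade leads to one instruction. State whether the items in 5.3.1 are mandatory or discretionary, and make the cross-references in 6.1.5 (both arms), 7.1.1, 7.3.2 and 7.3.3 match. State which passage takes precedence where a general item and a table row both apply. Which rule to adopt is for the sponsor's clinicians; this review proposes none. The cost is amendment wording or a clarification letter to sites. Sample size, event count and planned tests do not change.
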